# 6 Potential Risks and Benefits

## 6.1 Risks

The main acute adverse effects of narrowband UVB (NB-UVB) are erythema and induction of photosensitivity diseases, such as polymorphic light eruption (PLE). Although the risk of erythemal episodes may be increased by concomitant phototoxic drugs, this can be minimized by undertaking a baseline minimal erythema dose (MED) and establishing treatment protocols based on an individual's MED. This also allows any unsuspected abnormal photosensitivity diseases to be detected, in particular solar urticaria or chronic actinic dermatitis (CAD). Induction of PLE may occur during a treatment course but generally can be accommodated via dose adjustments and judicious use of topical corticosteroid, without the need to stop NB-UVB. Other uncommon side-effects, such as psoriatic lesional blistering, occasionally occur but generally treatment is very well-tolerated.

Overexposure to our artificial UVB source may incur similar symptoms to a mild sunburn (slight reddish coloration to the skin). The Solius Photobiological System was designed to minimize total UVB exposure to minimize the potential for sunburn. To make sure subjects do not develop redness (erythema) or blistering, the exposure will set for the lamp to 60% or 0.60 of the minimal erythemal dose (MED) for each individuals' skin type.

Over exposure to the UVB to the eyes may cause photokeratitis. To prevent the overexposure, the subject's dosage will be determined during titration period. Eye protection will be provided to the subject in the device before each treatment. The device software will require that the subject physically obtained the eye protection from the dispenser in the device before the device can be turned on to emit the UVB light. An additional safety feature of the device is the height of the emitting lens is 51". Testing conducted by 3rd party showed that there is almost 0 UV output at 56" from the floor. Thus, little or no radiation is emitted above the height of 5 feet and therefore the face and eyes will not be exposed to the UVB light if for some reason the subject does physically place the eye protection shield over his/her eyes. This is demonstrated in the enclosed picture of the device along with its other features.

The UV light panel height is 51 inches.

As the appropriate doses are individualized to the subject, to establish the correct dose, each subject will complete a titration period of up to 5 weeks. The titration period will start with an erythemally weighted dose of 10.53 mJ/cm2 to 43.07 mJ/cm2 (depending on skin type) and increase by 26 – 36% each step until a maximum erythemally weighted dose of 34.88 mJ/cm2 – 109.33 mJ/cm2 (depending on skin type). If the subject shows a skin reaction i.e erythema, the dose will be reduced to 60% of the dose that caused the skin reaction/erythema.

The subject's dosage will be administered under conditions of full-body exposure except the face (males in swimming trunks or briefs and females in bikini or bra and panties) of 0.6 minimal erythemal dose (MED) once per week for 16 weeks. At each visit, the subject will report adverse events and any skin changes.

The PI will be available to the study staff member to answer any questions or concerns from potential subjects prior to consenting. We will have the blood samples drawn by trained professionals to minimize the risk of hematoma formation, bleeding, or infection at the site of needle insertion. Study staff will update subjects in a timely way on any new information that may affect their health, welfare, or decision to stay in this study. Any and all side effects reported will be recorded in the subjects' file in the study binder. Subjects will be instructed to call the study staff immediately if any side effects do occur. The PI will advise the study staff who have received the information from the subject as to how this side effect should be handled, recorded and reported. After the determination, all samples will be de-identified. We have a plan to protect subject privacy and confidentiality, which is explained in the plan to protect subject privacy and confidentiality in the data section.

Vitamin D deficiency and insufficiency is common in adults due to an inadequate dietary intake of vitamin D and or inadequate sun exposure. Chronic (years to decades) vitamin D deficiency and insufficiency can lead to bone loss resulting in increased risk of fracture later in life. Chronic vitamin D

deficiency can also cause a mineralization defect of the skeleton resulting in osteomalacia. Short term (6 months) vitamin D deficiency and insufficiency is not associated with significant bone loss or osteomalacia. Therefore, the participants, especially those who are in the sham treatment group, are at no increased risk for fracture or osteomalacia. At the termination of this study those participants who were in the sham group will be encouraged to take a vitamin D supplement along the guidelines recommended by the Endocrine Society to correct their vitamin D deficiency and insufficiency.

Chronic excessive exposure to sunlight or ultraviolet radiation for prolonged periods of time, in years or decades, can increase risk for nonmelanoma skin cancer. To minimize the risk the subjects will be 22 years and older and will be exposed to suberythemal doses of UVB radiation for the duration of the study

# 6.2 Potential Benefits

The study participants may receive no benefit. All participants in the study will know that they are vitamin D deficient/ insufficient because that will be a requirement for being enrolled in the study. The control group will only know their vitamin D status and will receive no additional benefit for participating in the study. The group exposed to the Solius Photobiological System's UVB light may improve their vitamin D status because the UVB emitting lamps are designed for producing vitamin D in the skin similar to sunlight. Results from this study will provide scientific knowledge regarding this devices ability to produce vitamin D and improve vitamin D status in people with vitamin D deficiency such as subjects with fat-malabsorption syndromes. All subjects will be evaluated for vitamin D deficiency will be advised to take a vitamin D supplement along the guidelines recommended by the Endocrine Society Practice Guidelines on Vitamin D. Alternatively, if they do not wish to take a supplement and would like a prescription for vitamin D we will contact their primary care doctor and inform them of their vitamin D status so that they can prescribe the appropriate vitamin D treatment as recommended by the Endocrine Society's Practice Guidelines on Vitamin D.

Subjects will not be responsible for any research related costs. They will receive compensation in each of their visit, which is shown below. Parking vouchers or transportation cost are available for each visit.

Study		Post-int	Total			
group/activity	Wk	Wk	Wk	Wk		
	22	23	24	25		
Activity	BD	BD	BD	BD	\$1550	Up to
(both treatment						2,330
group and sham						
control group)						
Compensation	\$50	\$50	\$50	\$250		
Transportation	PV	PV	PV	PV or	Up to	
cost up to	or	or	or	up to	\$780	
	up	up	up	\$30		

Study	Screening		٦	Fitratio	۱									Interv	ention							
group/activity	visit	Wk	Wk	Wk	Wk	Wk	Wk	Wk	Wk	Wk	Wk	Wk	Wk	Wk	Wk	Wk	Wk	Wk	Wk	Wk	Wk	Wk
		1	2	3	4	5	6	7	8	9	10	11	12	13	14	15	16	17	18	19	20	21
Activity	Screening	UV	ŪV	UV	UV	UV	UV	UV	UV	UV	UV	UV	UV	UV	UV	UV	UV	UV	UV	UV	UV	UV
(both treatment	Consent					BD				BD				BD				BD				BD
group and sham	BD																					1
control group)																						1
Compensation	\$100	\$50	\$50	\$50	\$50	\$50	\$50	\$50	\$50	\$50	\$50	\$50	\$50	\$50	\$50	\$50	\$50	\$50	\$50	\$50	\$50	\$50
Transportation	PV or up	PV	PV	PV	PV	PV	PV	PV	PV	PV	PV	PV	PV	PV	PV	PV	PV	PV	PV	PV	PV	PV
cost up to	to \$30	or	or	or	or	or	or	or	or	or	or	or	or	or	or	or	or	or	or	or	or	or
		up	up	up	up	up	up	up	up	up	up	up	up	up	up	up	up	up	up	up	up	up
		to	to	to	to	to	to	to	to	to	to	to	to	to	to	to	to	to	to	to	to	to
		\$30	\$30	\$30	\$30	\$30	\$30	\$30	\$30	\$30	\$30	\$30	\$30	\$30	\$30	\$30	\$30	\$30	\$30	\$30	\$30	\$30

Note: BD: Blood draw; UV: Ultraviolet B radiation exposure or sham control Blood samples will be collected after each UV exposure.

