## 8 Study Intervention

The treatment group (n=40) will be exposed to the Solius Photobiological System, and the control group (n=40) will receive the same procedure with only the blue/purple LEDs. The study intervention will involve an investigational UVB emitting device, The Solius Photobiologic System created by Solius. The Solius Photobiological System emits UVB to make sure subjects do not develop redness, the exposure will set for the lamp to 60% or 0.60 of the minimal erythemal dose (MED) for each individual's skin type.

As the appropriate doses are individualized to the subject, to establish the correct dose, each subject will complete a titration period of up to 5 weeks. The titration period will start with an erythemal weighted dose of 10.53 mJ/cm2 to 43.07 mJ/cm2 (depending on skin type) and increase by 26 - 36% each step until a maximum erythemal weighted dose of 34.88 mJ/cm2 – 109.33 mJ/cm2 (depending on skin type) or the subject shows a skin reaction. This dose will be the subject's dosage.

The device will have a strip of blue/purple LEDs installed inside the light towers. For users that are defined in the treatment group, both UV lamps and purple LED will turn on during the treatment. For users that are defined in the control group, they will go through the same pre-treatment workflow. However, when the user hits start treatment, only blue/purple LEDs will turn. The times that the control subjects will be in the sham operational device mode for the titration phase and 16-week treatment phase will be the same as those in the intervention UVB device mode based on skin type. According to a previous study by Solius where 43 subjects were exposed to a 0.6 MED, the stimulation of cutaneous vitamin D and subsequent increase in serum concentration of 25(OH)D from phototherapy was compared to the effect of a Recommended Daily Allowance (RDA) based dose of 600 IU vitamin D3 supplement daily for 10 weeks. Thus we will expose these individuals a 0.6 MED once per week for 16

weeks to observe the effect on 25(OH)D serum concentration. Serum 25(OH)D concentration will be monitored until 4 weeks after the intervention.

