## 10.2 Safety Review

[name] or [name] will interview the subjects in the intervention and sham groups before their next exposure each week for any adverse events including erythema or any other skin reactions. At the time of the evaluation, it will be determined whether the subject will continue with the next exposure or whether the subject will be removed from the study. This will be based on the determination of the degree of erythema or adverse skin reaction.

In addition, Prior to each treatment, Solius software will prompt the user with the following questions to assess erythema:

- 1. Did you observe any pinkness (similar to sunburn) after your last treatment? (yes / no)
- 2. Did the pinkness last for more than 3 days? (yes / no)

3. Did you experience any pain or discomfort (excluding itch) with the pinkness? (none / mild / moderate/ severe)

Based on the user's response, the software could maintain current dose, reduce dose, or block account for further investigation. The PI or [name] or [name] will be notified to perform further assessment if an account was blocked by the software.

Side effect	Signs/symptoms	Instruction for subjects on
		monitoring
Sunburn	Pain, tenderness of the	Check for pain and redness 4-6
	skin, redness, tightness,	hours after treatment. If there
	itching, and rarely	is severe pain, should seek
	blistering	medical attention.
		If there are blisters, should seek
		medical attention
Photoaging	Atrophic skin, coarseness,	If there is increased fragility (i.e.
	fibrotic areas, increased	easy bruising or tearing of skin),
	fragility, laxity, mottled	then should seek medical
	pigmentation,	attention. The other
	telangiectasias, wrinkling	photoaging side effects are
		benign and more of a cosmetic
		nature.
Tanning	Skin darkening	As a benign side effect, no
		subject monitoring is needed

The following known side effects of UVB will be monitored:

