# 10.4 Stopping Rules

A subject will be withdrawn from the study if refuse to participate, or if the subject undergoes an adverse reaction to the light source e.g. skin erythema or pruritus.

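### Payment is per visit and Section 10.4, read literally, withdraws a subject for a skin reaction, so reporting a titration reaction could cost about 74–87% of $1,550; payment and follow-up after such a stop should be protected

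*Combined protocol and SAP*

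**What the plan says.** **Payment.** Section 6.2 states "They will receive compensation in each of their visit, which is shown below". Its tables list $100 at screening, $50 at each of Weeks 1 to 24 and $250 at Week 25, totalling $1,550. Transport of up to $780 brings the ceiling to $2,330. No payment rule is given for a subject who is withdrawn.

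**What follows a skin reaction.** Five sections speak to this and do not agree:

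- Section 10.4: "A subject will be withdrawn from the study if refuse to participate, or if the subject undergoes an adverse reaction to the light source". Erythema and pruritus are its examples. There is no severity threshold and no exception for titration.
- Section 10.2: before each weekly exposure, "it will be determined whether the subject will continue with the next exposure or whether the subject will be removed from the study", according to the degree of reaction. Separately, the device software may keep the dose, lower it or block the account.
- Section 6.1: "If the subject shows a skin reaction i.e erythema, the dose will be reduced to 60% of the dose that caused the skin reaction/erythema".
- Section 8: titration steps up to a maximum "or the subject shows a skin reaction. This dose will be the subject's dosage".
- Section 6.3: the intervention stops for reactions classed as significant. Simple redness is not on its list.

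**How reactions become known.** Section 6.1 says "At each visit, the subject will report adverse events and any skin changes" and tells subjects to telephone at once about side effects. The Section 10.2 software asks "Did you observe any pinkness (similar to sunburn) after your last treatment", and staff interview the subject before the next exposure. Section 6.3 adds that subjects are questioned and examined at every exposure.

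**The concern.** A subject who believes that admitting to redness may end participation, and with it most of the payment, has a reason to stay silent. The reactions most exposed to this are those that appear and fade between weekly visits, because staff then have only the subject's word.

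Two results lean on these reports. Safety is a stated objective, and Section 4.1.1 tabulates the reported events. Titration uses the skin reaction to end escalation or lower the dose, so an unreported reaction would let the dose step up again, as far as the skin-type maximum. Genuine UVB reactions can arise only in the UVB arm, so concealing them would narrow the difference between arms in the direction that favours the device.

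There is also an effect on efficacy. Withdrawal from the study, as opposed to stopping exposure, ends blood sampling. Section 12 calls for an intention-to-treat analysis of conversion after 16 weeks of treatment, measured at Week 21. Withdrawals for a light reaction would remove Week 21 values mainly from the UVB arm.

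**Working it through.** **1. Reproduce the stated total (Section 6.2).**
Screening 100 + Weeks 1–21 (21 × 50 = 1,050) + Weeks 22–24 (3 × 50 = 150) + Week 25 (250) = $1,550, as stated. Transport: 26 visits × 30 = $780. Sum: $2,330, as stated.

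**2. Amount lost if Section 10.4, or a removal under Section 10.2, is applied.**
Under Section 10.2 a reaction is asked about before the next weekly exposure, so reactions to the titration exposures of Weeks 1–5 are reported at Weeks 2–6. Assume that the reporting visit is paid and every later visit is lost.
Paid by Week w = 100 + 50w. Lost = 1,550 − (100 + 50w) = 1,450 − 50w.

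| Reported at | Paid | Lost | Share of $1,550 |
|---|---|---|---|
| Week 2 | $200 | $1,350 | 87.1% |
| Week 3 | $250 | $1,300 | 83.9% |
| Week 4 | $300 | $1,250 | 80.6% |
| Week 5 | $350 | $1,200 | 77.4% |
| Week 6 | $400 | $1,150 | 74.2% |

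The 74% end belongs to Week 6, the first intervention visit. Reports made at the titration visits themselves (Weeks 2–5) give 77% to 87%.

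**3. Sensitivity to the unstated payment rule.**
- Reporting visit not paid: the loss is $50 more, so 90.3% (Week 2) to 77.4% (Week 6).
- Withdrawn subject still attends and is paid for Weeks 22–25 (3 × 50 + 250 = $400; the documents do not say this): the loss is (1,050 − 50w)/1,550, so 61.3% to 48.4%.
- Sections 6.1 or 8 applied instead (dose reduced or fixed, subject continues): the loss is $0.

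**4. Illustration of what concealment could do to a comparison of reactions.**
The true risk, the concealment shares and the test are assumptions, because the protocol only tabulates adverse events. Take 40 per arm, no sham reactions and a two-sided Fisher test at 0.05. Against 0/40, five events give p = 0.055 and six give p = 0.026, so six are needed. P(X ≥ 6) for X ~ Binomial(40, recorded rate), with a true UVB risk of 20%:
- All reported (recorded 20%): 0.84.
- A quarter concealed (15%): 0.57.
- Half concealed (10%): 0.21.

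Only the recorded rate matters here. A true risk of 40% with half concealed also gives 0.84, and a true risk of 10% with nothing concealed gives 0.21. The figures show how sensitive such a comparison would be; they do not predict behaviour.

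**The case against.** The strongest reply is that the rules written specifically for titration keep the subject in. Section 6.1 lowers the dose and Section 8 makes the reaction the end of titration, so under either the loss is nil. Applied literally, Section 10.4 would remove the very subjects whose reactions Section 8 uses to set a dose. **This stands.** A reader might infer that a reported reaction leads to withdrawal as a matter of course. The documents do not support that: it follows only from Section 10.4 or a removal under Section 10.2. It does not dispose of the point, because Section 10.4 is the stopping rule, its wording is mandatory, and a subject answering the software questions cannot know which section will be applied.

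A reader might also infer that the safety data are purely self-reported, or that reactions are in fact being concealed. Neither is supported. Subjects are examined at each exposure and told to telephone about side effects, so the gap is limited to reactions that fade between visits and are not phoned in. The documents contain no data on under-reporting.

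Other replies also carry weight:
- The consent pages were not available for this review and may already state what is paid after withdrawal.
- Section 9 allows early exit with no change in procedure and a final blood sample before removal. That is ambiguous about later visits, and no payment for the sample is stated.
- Payment is the same in both arms and subjects are blinded, so itch or perceived pinkness under sham faces the same incentive. The asymmetry concerns genuine UVB reactions only.
- Dose cannot rise without limit, because Sections 6.1 and 8 cap it by skin type.

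**Conclusion.** The point holds conditionally. If Section 10.4, or a removal under Section 10.2, is applied to a reaction reported at Weeks 2 to 6, and later visits are therefore lost, the subject forfeits about 74% to 87% of $1,550. This assumes that the reporting visit is paid and that no unseen consent wording protects the rest. Under Sections 6.1 and 8 the loss is nil.

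What follows is a possible incentive to under-report transient reactions, of unknown size, and a loss of Week 21 outcomes mainly from the UVB arm. The 0.84, 0.57 and 0.21 figures should not be read as an estimate of harm to this trial, since no safety test is planned or powered and the input rates have no source in the documents. Severity is low to moderate. The change is still worth making, because it is cheap and serves both the safety data and the intention-to-treat analysis.

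**What to change.** 1. Reconcile Sections 6.1, 6.3, 8, 10.2 and 10.4 on what follows a skin reaction. No view is taken here on which clinical rule is right.
2. Whatever rule is kept, amend Section 10.4 to separate stopping exposure from leaving the study, so that a subject whose exposure is stopped for a reaction may attend the remaining scheduled adverse-event and blood-draw visits, including Weeks 21 to 25.
3. State in Section 6.2, and in the consent if it does not already say so, that each of those visits is paid at the listed amount, including the $250 at Week 25.
4. Tell subjects before the first session that reporting a reaction does not reduce payment.

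Reconciliation alone is not enough: any rule that still permits removal leaves payment unprotected.

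**Cost.** Wording in Sections 6.2 and 10.4, and possibly the consent; some visits without exposure; and less money saved on subjects who stop. Spending stays within the $2,330 per subject already set. Slight over-reporting is possible, limited because visits must still be attended and skin is examined. In return, Week 21 values are kept for subjects who stop exposure.

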## 6.3 Analysis of Risks in Relation to Benefits

Highly trained professionals will be performing the blood draws which is likely to be a chance of risk. The adverse skin reaction from the Solius Photobiological System such as skin erythema and pruritus is a possible risk in this study. However, this study will expose the participants to a relatively low intensity of UVB (0.6 MED), so the risk of adverse reaction is minimal. All the participants will be asked for their willingness to receive the intervention at every exposure and will be questioned and examined for any potential adverse reaction due to the intervention. If any significant adverse reaction is detected, the intervention will immediately stop and the affected participant will receive immediate medical attention. Significant adverse reactions include photokeratitis, moderate to severe skin tenderness, itchness and tightening, skin blistering, or bruising or tearing of skin. The risks of breach of confidentiality are highly unlikely, and therefore benefits will greatly outweigh the risks.

## 7 Study Subject Selection

## 7.1 Subject Inclusion Criteria

In order to be eligible to participate in this study, an individual must meet all of the following criteria:

- 1. Age at least 22 years old
- 2. Male or Female
- 3. Skin Type I-VI
- 4. Women of child bearing potential must be on birth control and not pregnant based on a negative pregnancy test at baseline.
- 5. Ability and Willingness to give informed consent and comply to protocol requirements
- 6. Serum total 25(OH)D < 30 ng/mL

# 7.2 Subject Exclusion Criteria

An individual who meets any of the following criteria will be excluded from participation in this study:

- 1. Ongoing treatment with supplemental or pharmacological doses of vitamin D, vitamin D metabolites or analogues
- 2. Pregnant
- 3. History of underlying photosensitivity
- Use of medications that cause a photosensitivity reaction (including but not limited to): tetracycline, tretinoin, amiodarone, doxycycline, naproxen, diphenhydramine, methotrexate, and hydrochlorothiazide
- 5. History of skin cancer
- 6. Plan to received significant sun exposure below the 33rd parallel during study
- 7. Used tanning or phototherapy devices within the last 30 days
- 8. Vitamin D supplement use of more than 600 IUs daily.
- 9. Systemic steroids use
- 10. H1 antihistamine use in the last 7 days
- 11. Diagnosed with light allergies (including but not limited to): actinic prurigo, polymorphous light eruption, or solar urticaria
- 12. Diagnosed with light sensitivities (including but not limited to): protoporphyria, photodermatitis, xeroderma pigmentosum, lupus erythematosus, chronic actinic dermatitis, or UV-sensitive syndrome

